Hypothesis 1: Assuming a correlation of pre- and post-test conservatively: reliability of 300 followers will be required. If the correlation between pre- and post is larger, smaller sample sizes are required. Thus, a sample of 300 Blacks and 300 Hispanics is adequate to examine the within-subject change using a paired t-test. The pre-post-test for binary outcomes (% of isolates) is McNemar's test. The minimum required sample size is 208. Thus, the proposed sample sizes will be adequate to test within-group differences.

Hypothesis 2: The total minimum required sample size in each ethnic group (Black and Hispanic) will be 192 for a total of 385 with effect size 0.332 (Cohen's d). Assuming that α =0.05, 1- β =0.80 (power), the total minimum required sample size for the two groups (Black and Hispanic) with effect size 0.1525 (P_0 - P_1) is **318** (**159 per group**).

Data analysis: Extensive processing is required before the actual data analysis, which comprises data science methods and statistical tests for our hypotheses.

Data processing: We will process Twitter data for data analyses through several steps:1) merging of data files in our institutional high performance computing (HPC) environment (Habanero), 2) converting XML to txt file format into a human-readable format for integrity checking, 3) feature selection, and 4) indexing.³⁵

Data science analyses for publicly available de-identified data: We will use a variety of software packages (R, Python, Nvivo, ORA, NodeXL, SAS) for the data science analyses. Since Twitter user demographics and personal data are not directly available, we will apply algorithms to users' Tweets and images to estimate their demographics, including those considered Social Determinants of Health.³⁶⁻³⁹ We will stratify those variables into categories for data analysis procedures as relevant. To answer research question 1, we will descriptively characterize (e.g., #Tweets, # followers, #likes, #retweets) Twitter activity in the two networks. To address the second research question, we will apply Syuzhet sentiment analysis and LDA to characterize negative affect scores and topic models, respectively. For the third research question, we will compute the network measures listed in **Table 1**.

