Emotional valence, expressing topics, and conversational styles in macro-,meso- and micro-level among de-identified Twitter followers will be computed from publicly available Tweet data. Unlike the traditional methods, data science methods such as natural language processing (NLP) and network analyses enable us to detect emotional valence score, changes in topics, volume of isolates, and communication styles without asking the users any questionnaires. The following table summarizes concepts, measurements, units of analysis, and data science analytic methods.

Table 1. Concepts, Measures, Data Science Methods and Units of Analysis

	Concept	Measures [§]	Data Science Methods	Unit
Content	Emotional valence ⁴⁰	Emotional valence score ^{18, 40-45} detected from text data (e.g., "This is so helpful" – emotion score +4, "I am sad"- emotion score -6)	Syuzhet packages 46	***
	Social support (informational, instrumental, emotional, appraisal)	Topic changes in social support ^{17, 19-21}	Topic modeling using hierarchical ⁵¹ and n-gram embedded LDA algorithms ⁵¹⁻⁵⁴	***
ø)	Social network: Macro- level ⁵⁵	The volume of isolates, Network type, Density, Centralization, Cohesiveness 26, 27, 55, 56	Network analysis ¹⁷⁻ 20, 23, 24, 26, 27	***
Structure	Social network: Meso- level ^{57, 58}	Size and number of communities, the volume of the community activities, leaders of community ^{26, 27, 56, 57}	Clauset-Newman- Moore ⁵⁹ Girvan-Newman ⁵⁸	**
	Social network: Micro- level ⁶⁰	16 communication types among triad, number of individual posting activities 26, 27, 56, 57, 60	Triad census analysis ⁶⁰	*

^{*} individual level, ** community level, *** global network level, §all measures in real-time)

Statistical Analyses: Pre-post comparisons will be examined from baseline (3 months pre-intervention) to 3 months (9-12) months after initiation of the intervention. Analyses of pre-post mean differences will be performed using SAS PROC TTEST, PROC Mixed, PROC GLIMMIX, and PROC CATMOD, with adjustments for the correlation within participants induced by repeated measures and for unreliability and missing data treatment. The continuous outcome will be analyzed using SAS PROC TTEST, PROC Mixed, and the binary outcome will

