be analyzed using PROC GLIMMIX or PROC CATMOD (for the McNemar test), depending on the missing data. We will compare measures among the two groups using independent t-tests for continuous variables and Chisquare tests for proportions to test the second hypothesis. Machine learning-based trend analysis 61, 62 will be applied for the continuously detected emotional valence score.

[figure not shown]
3. Study Procedures

Procedure: Publicly available Tweet data (e.g., Tweets, time stamp, self-reported location) from de-identified Twitter followers of our Twitter sites will be obtained from the public database. No personally identifiable information (PII) under the definition used by the National Institute of Standards and Technology (NIST) such as names, addresses, date of birth, and email addresses will be collected. We will analyze publicly available Tweet data for emotional valence (auto-estimation from Tweet messages), topic changes, the volume of isolates, size and number of communities, and communication types for our outcome variables. In addition, three demographic elements (i.e., self-reported age, gender, race/ethnicity, which are un-linkable to their PIIs) will be collected to examine general confounders. Again, no PII will be used or accessed.

Intervention: Two Tweeters, including a bilingual Hispanic, will strictly follow the intervention delivery protocol developed in Aim 2 with guidance from the Tweet-S2 Expert Panel. Daily for 365 days that cross Years 3 and 4, the Tweeters will post a Tweet from the Tweet library to each Twitter community alternating among those related to information, instrumental, emotional, and appraisal support. The Tweeter will also engage in social network activities by replying to, liking, and retweeting messages posted by others. This intervention will be consistently conducted (e.g., time, center brand themes, designs) to enhance intervention fidelity.⁶³ After a Tweet is posted, followers can respond using Twitter functions (e.g., retweet to quote and disseminate our Tweet message, posting a Tweet message to express their after thoughts and questions using @mention, like. and reply function). In addition, the P.I. will examine the archive files to monitor intervention fidelity and reinforce expected behaviors of the Tweeters as needed.

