Considering 60% attrition rate of anonymous online users, we anticipate to enroll >400 per group, to accrue up to a total of 800 (400 per group, total minimum required Sample are 318 users: 159 per group) and retain anonymous followers (no actual name or phone number/email address on the profile or Twitter handle) for our Twitter communities in multiple ways: 1) A flyer will be distributed up to 5 times (per a week) via an email to the caregivers, who agreed to be contacted for the future studies, in the dementia caregiver registries; 2) we will use an online advertising function for marketing our Twitter communities using TwitterAds (15 days in Year 3 and 15 days in Year 4); 3) research flyers will be posted in relevant clinics (i.e., AIM clinic and neurology units at CUIMC); 4) using the @mention function, we will ask the community leaders (e.g., @alzassociation, which has 107K followers) to post our flyer; and 5) every month, we will contact relevant community leaders within Twitter to post our flyer. This study does not offer any incentives (e.g., no online credits, no monetary compensation).

8. Informed Consent with waiver of documentation (45 CFR 46.116)

Informed consent will be obtained with a waiver of documentation (e.g., signature). Anonymous Twitter users without PII (no name, email address, phone number, or addresses are linkable) will participate in this study, analyzing publicly available de-identified data. Accidental PII exposure will be strictly prohibited (see four strategies in privacy protection) and monitored daily. Therefore, this research to post social

support messages to our Twitter network followers involves minimal risk to the subject. The signature on the informed consent document would be the only record linking the subject to the research.

9. Confidentiality of Study Data

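### Enrolment of 400 per group covers only the smallest stated minimum: after the plan's own 60% attrition 160 per group remain, against the 300 stated for the Hypothesis 1 paired t-test

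*Combined protocol and SAP*

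**What the plan says.** Section 2 (The setting, Sample, and Power Analysis) expects more than 400 followers in each network and does not mention attrition. It then gives four minimum sizes.

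- **Hypothesis 1, continuous (pre-post, within group).** "Thus, a sample of 300 Blacks and 300 Hispanics is adequate to examine the within-subject change using a paired t-test". The paragraph describes its correlation assumption as conservative and adds: "If the correlation between pre- and post is larger, smaller sample sizes are required". No correlation, effect size, alpha or power appears in the available text.
- **Hypothesis 1, binary (McNemar).** "The minimum required sample size is 208. Thus, the proposed sample sizes will be adequate to test within-group differences". The 208 is not labelled per group, but the test is a within-group one.
- **Hypothesis 2, continuous (Black versus Hispanic).** The size per ethnic group "will be 192 for a total of 385 with effect size 0.332" (Cohen's d). No power is attached to this figure.
- **Hypothesis 2, binary.** 159 per group, 318 in total, for a difference in proportions of 0.1525 at alpha 0.05 and 80% power.

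Section 7 is the only place where attrition enters: "Considering 60% attrition rate of anonymous online users, we anticipate to enroll >400 per group, to accrue up to a total of 800". In the same sentence it names just one of the four figures as the requirement: "total minimum required Sample are 318 users: 159 per group".

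On incomplete data, Statistical Analyses in Section 2 plans pre-post comparisons "with adjustments for the correlation within participants induced by repeated measures and for unreliability and missing data treatment", and says the binary outcome will "be analyzed using PROC GLIMMIX or PROC CATMOD (for the McNemar test), depending on the missing data".

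**The concern.** The recruitment target and the power section work from different requirements. Section 7 inflates the smallest of the four minimums for attrition. Section 2 declares the sizes adequate for Hypothesis 1, whose larger minimum was never inflated. Nothing in the document reconciles the two.

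Both networks receive the intervention, and Hypothesis 2 compares one network with the other. Hypothesis 1 is therefore where the plan tests whether anything changed after the intervention began. If that test runs on about half the pairs the plan says it needs, a non-significant result could be read as no change, on the strength of a document that describes the study as adequately sized.

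**Working it through.** **Inputs.** Attrition 60%, enrolment 400 per group and ceiling 800 come from Section 7. The minimums 300, 208, 192 and 159 come from Section 2. The follower is taken as the unit, as in the Hypothesis 1 paragraph, and 208 is read as per group.

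**1. Reproducing the plan's figure.** Enrolment = minimum/(1 − attrition) = 159/0.4 = 397.5, so 398, which rounds to the stated 400. The 400 is thus a pre-attrition number built on 159. The 159 is itself attainable: at two-sided alpha 0.05 and 80% power, a difference of 0.1525 gives exactly 159 per group when the lower proportion is about 0.305–0.311 or 0.537–0.542. The plan does not state the two proportions.

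**2. Retained against required.** Retained = 400 × (1 − 0.60) = 160 per group.

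| Test | Stated minimum n | 160 − n | Enrolment needed, n/0.4 | Highest attrition at 400, 1 − n/400 |
|---|---|---|---|---|
| H1 paired t-test | 300 | −140 | 750 | 25% |
| H1 McNemar | 208 | −48 | 520 | 48% |
| H2 continuous | 192 | −32 | 480 | 52% |
| H2 binary | 159 | +1 | 398 | 60.25% |

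Meeting 300 would take 2 × 750 = 1,500 followers, against a ceiling of 800.

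**3. Power for Hypothesis 1.** The basis of 300 is not given, so two-sided alpha 0.05 is assumed and two cases are shown (noncentral t; the standardised change is the mean change divided by the SD of the changes).

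- If 300 was the 80% size, the implied standardised change is 0.162, and 160 pairs give 53% power.
- If 300 was the 90% size, it is 0.188, and 160 pairs give 66%.
- At 80% power, 160 pairs detect a standardised change of 0.223.

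For McNemar, normal scaling gives Φ[(1.960 + z)√(160/208) − 1.960]. This is 69% if 208 was the 80% size (z = 0.842) and 81% if it was the 90% size (z = 1.282).

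**4. Hypothesis 2, continuous.** At d = 0.332 and two-sided alpha 0.05, 80% power needs 144 per group, 192 gives 90%, and 160 gives 84%. Missing the 192 costs little.

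**5. Could a larger correlation close the gap?** The required number of pairs is proportional to 1 − r. If 300 assumed correlation r0, 160 pairs suffice only when the true r is at least 1 − (1 − r0) × 160/300. This is 0.47, 0.63 or 0.73 for r0 = 0, 0.3 or 0.5.

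**6. Could a mixed model close it?** Suppose all N = 400 have baseline data, n = 160 have both occasions, and missingness is ignorable. In units of the outcome variance, the variance of the estimated change is 1/N + (1 − r²)/n + r²/N − 2r/N, and effective pairs = 2(1 − r)/variance.

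- r = 0: 2/0.00875 = 228.6
- r = 0.3: 1.4/0.0069125 = 202.5
- r = 0.5: 1/0.0053125 = 188.2

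All are below 300. If 300 was the 80% size, power is about 68%, 63% and 60%.

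**The case against.** The 300 cannot be verified. The sentence that introduces it is garbled, possibly by text loss, and its inputs are missing. The plan calls its assumption conservative and says a larger correlation would lower the number. On this view an unreconciled contradiction is proven, but an underpowered test is not. That is fair, and the power figures above are conditional for this reason. The plan still offers no smaller number, and nothing in it supports the correlations that 160 pairs would need.

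The timing of attrition is not stated, and the post-test window is months 9–12. If losses accrue over the year, followers who leave late already have some post-test data. About 400 × 0.4^0.75 = 201 per group would remain at month 9 under a constant hazard, or 400 × (1 − 0.6 × 0.75) = 220 under linear loss. Then 192 is met in both cases and 208 under linear loss, so those two shortfalls depend on timing. The shortfall against 300 does not. Nor does it vanish if the 60% was meant as retention: 240 remain, giving about 71% or 83% power on the 80% or 90% basis.

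The mixed-model figures allow only two occasions, whereas tweets are collected daily. A longitudinal model with intermediate data could recover more. At r = 0.5, however, reaching 300 would need baseline and intermediate data, available on all 400, to explain about 78% of the post-test variance, and the plan specifies no such model. The most favourable case is that 300 was a 90% size at zero correlation: a two-occasion mixed model would then give about 81% power, a basis the sponsor would have to document.

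Two readings remain uncertain. If 208 is a total (104 per group), 159 is no longer the smallest minimum. The measures table in Section 2 also places emotional valence and isolates at global network level, while the power section counts followers. Neither removes the mismatch between 160 and 300.

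Finally, no passage names Hypothesis 1 as primary, and the remedy is only wording. That keeps the cost low. It does not make the adequacy statement correct.

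**Conclusion.** The concern holds. On the plan's own attrition rate and accrual ceiling, 160 followers per group remain, 140 (47%) fewer than the 300 it says the Hypothesis 1 paired t-test requires. The claim that the sizes are adequate for within-group differences is not supported as written. This conclusion needs only the plan's own figures.

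The loss of power is less certain: about 53% or 66% for complete pairs, depending on whether 300 was an 80% or 90% size at two-sided alpha 0.05, with some recovery possible from a mixed model or a higher correlation. The shortfalls against 208 and 192 are secondary. The first depends on the per-group reading, both depend on when attrition occurs, and Hypothesis 2 for the continuous outcome keeps about 84% power.

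**What to change.** Keep enrolment at 400 per group and correct the text, in this order.

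1. **Section 2, all four minimums.** State or confirm the alpha, power and effect size behind each, the pre-post correlation behind 300, and whether 208 is per group. The 192 is consistent with 90% power at d = 0.332. The sponsor should confirm that basis, and the figure need not be replaced. Say when the 60% attrition is expected to occur.
2. **Section 7.** Replace 318 (159 per group) as the overall minimum with the binding stated one, 300 per group for Hypothesis 1 unless step 1 changes it, and say that it is not met after 60% attrition. Keep 159 in Section 2, labelled as the Hypothesis 2 binary minimum.
3. **Section 2, Hypothesis 1.** Replace the adequacy sentence with what about 160 retained pairs deliver: a detectable standardised pre-post change of about 0.22 at 80% power and two-sided alpha 0.05, with the assumed correlation stated. Add the corresponding McNemar power from the sponsor's own assumptions about discordant pairs.

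The cost is redrafting the power and recruitment text. Enrolment, data collection and analysis do not change. The stated sensitivity for Hypothesis 1 becomes less favourable.

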Publicly available Twitter data collection: During the baseline (3 months pre-intervention) and intervention (365 days crossing Years 3 and 4) periods, we will collect publicly available Tweet messages and associated metadata (e.g., userID, relationship, time stamp, Tweet, Hashtags, Twitter page, geo code, location, type) daily. We will also double-check the data integrity (e.g., incompletely captured data) daily. In terms of missing Twitter data,⁶⁴ we will make an effort to minimize missing data in 3 ways: our designated Tweeters and the P.I. will be available during data collection, two collection tools (NodeXL and NCapture) will be used, and collection of Tweets will be monitored daily to ensure that capture was adequate and with no PII. Figure 1 shows an example of publicly available data collected.

Figure 1. An example of publicly available data collected via NodeXL: Vertex 1 and 2 will be used for macro, meso, and micro level network analyses. Tweet text with no personal identifiers will be used for text analyses, including emotion score calculation and topic modeling.

upon following Twitter networks

will be strictly prohibited and daily monitored/removed.

4. Study Drugs or Devices

Not applicable

5. Study Instruments (e.g., Questionnaires, Interview Outlines, Focus Group Guides) **No direct instrumentations** such as questionnaires (i.e., survey, interview) will be applied for the outcome measurers. Instead, emotional valence, topics, and conversational styles in macro-,meso- and micro-level among **anonymous Twitter followers** will be computed from the publicly available Tweet data. Unlike the traditional methods, data science methods such as natural language processing (NLP) and network analyses enable us to detect emotional valence score, changes in topics, volume of isolates, and communication styles without asking the users. Table 1 above in Data Analyses summarizes concepts, measurements, units of analysis, and data science analytic methods.

6. Study Subjects

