Inclusion criteria: The anonymous dementia caregivers must be 18 years of age or older, Black or Hispanic, living in the U.S. including the U.S. territories, a dementia caregiver with any duration, able to speak English or Spanish/bilingual. The participants must agree to terms of conditions of use and privacy policy and rules of one of the two dementia caregiver networks (Hispanic and Black), the Twitter user agreement of the terms of service, Twitter privacy policy, and Twitter rules, including intellectual property, violence, misconduct, abusive behavior, private information and spam and security, and use a smartphone or a feature phone (i.e., a cell phone with text messaging).

Screening/Determining Eligibility

Upon a Twitter user follows one of our Twitter networks after seeing our advertisement on Twitter or our flyers from our clinics and emails, our team will automatically receive a new follower notification from Twitter. Within 24 hours during the weekdays (72 hours during the weekend), our Tweeter/coordinator will send a screening message via the direct message function in Twitter (script attached) and respond if they are eligible to participate in our research Twitter networks (script attached).

When a Twitter user meets our inclusion criteria, the study staff will remind the user regarding our Twitter networks as a research study, voluntary participation, and unfollowing our Twitter networking sites at any time. Furthermore, using the direct message function via Twitter, our study staffs will ensure that the eligible user 1) creates an anonymous Twitter handle if the person uses his/her full name as a Twitter handle, and 2) hides their names from the profile setting. When a Twitter user does not meet our inclusion criteria, our study staff will request them unfollowing our Twitter network via a direct message function (script attached). Ineligible followers will be blocked within 72 hours after the unfollowing request.

7. Recruitment

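### Both powered outcomes need public Tweets, but the sample sizes count followers, eligibility requires neither a public account nor posting, and 60% attrition leaves a margin of one follower per group.

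*Combined protocol and SAP*

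**What the plan says.** **Outcomes.** Section 2 (power analysis) names two outcome variables for the hypotheses: emotional valence (continuous) and percentage of isolates (binary). Section 5 says that no questionnaires are used and that the measures "will be computed from the publicly available Tweet data". Valence is scored from Tweet text. Section 1 describes isolates as Tweets that received no response.

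**Sample sizes.** For Hypothesis 2, the binary calculation reads "Assuming that α =0.05, 1- β =0.80 (power), the total minimum required sample size for the two groups (Black and Hispanic", and continues "with effect size 0.1525 (P_0 - P_1) is 318 (159 per group". The continuous calculation "will be 192 for a total of 385 with effect size 0.332 (Cohen's d". For Hypothesis 1, "a sample of 300 Blacks and 300 Hispanics is adequate to examine the within-subject change using a paired t-test", and McNemar's test needs at least 208.

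**Accrual.** Section 7 reads "Considering 60% attrition rate of anonymous online users, we anticipate to enroll >400 per group", and goes on "to accrue up to a total of 800 (400 per group, total minimum required Sample are 318 users: 159 per group".

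**Eligibility.** Section 6 begins "The anonymous dementia caregivers must be 18 years of age or older, Black or Hispanic, living in the U.S" and adds caregiving, language, acceptance of terms and phone type. It does not mention a public account or posting. New followers are screened by direct message. Those who do not qualify are asked to unfollow and are then blocked.

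**Missing data.** Section 3 treats missing data as a capture problem. The Statistical Analyses paragraph mentions missing data treatment without specifying it. Nothing says how a follower with no Tweets is counted.

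**The concern.** A follower who only reads, or whose Tweets are protected, meets every listed criterion and takes a place in the accrual count, yet has no valence score and no Tweet to classify as an isolate. The sample sizes are useful only as counts of followers who have an outcome. If the single loss allowance is meant for people who leave the networks, nothing is set aside for people who stay and say nothing.

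At stake is the power of the between-group comparison and, more sharply, of the within-group tests. The paired t-test and McNemar's test need an outcome in both the 3-month baseline and months 9-12, so silence in either window removes the pair. The handling of a follower without Tweets also matters. If such followers were classed as isolates, the percentage of isolates would partly measure how many followers only read.

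**Working it through.** **Inputs from the plan:** 400 per group; 60% attrition; minimum 159 per group; difference in proportions 0.1525; d = 0.332; α = 0.05; power 0.80. **Not in the plan:** the base rate of isolates, whether tests are two-sided, and the share f of retained followers who are public and post. I assume two-sided tests and show ranges for the other two.

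**Step 1. Reproduce the accrual figure.** 159 / (1 − 0.60) = 397.5, so 398 per group and 796 in total. The plan's 400 and 800 match after rounding.

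**Step 2. Reproduce the 159.** The pooled two-proportion formula for a difference of 0.1525 at 80% power gives 159 when the higher rate is about 0.46 or 0.69. At 0.70 v 0.5475 it gives 158. The stated figure is compatible with these rates but cannot be confirmed, because no base rate is given.

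**Step 3. Find the margin.** 400 × 0.40 = 160 retained, one more than 159.
- If the 60% means leaving the network, 159 / 160 = 99.4% of those retained must be public and posting.
- If the 60% covers every kind of loss, 159 / 400 = 39.75% of those enrolled must give an outcome, and the target is met.

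**Step 4. Power under the first reading.** Evaluable n per group = 160 × f. With p̄ the mean of the two rates, isolate power = Φ{[0.1525√n − 1.96√(2p̄(1−p̄))] / √(p₁(1−p₁) + p₂(1−p₂))}. For example, with 0.70 v 0.5475 and n = 120: (1.6706 − 1.96 × 0.6851) / 0.6766 = 0.484, and Φ(0.484) = 0.69. Valence power uses the noncentral t with d = 0.332.

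| Assumed f | Evaluable per group | Isolates, 0.70 v 0.5475 | Isolates, 0.46 v 0.3075 | Valence, d = 0.332 | Enrolment per group for 159 evaluable, 159/(0.4f) |
|---|---|---|---|---|---|
| 100% | 160 | 81% | 80% | 84% | 398 |
| 90% | 144 | 76% | 76% | 80% | 442 |
| 75% | 120 | 69% | 68% | 73% | 530 |
| 50% | 80 | 51% | 51% | 55% | 795 |
| 25% | 40 | 29% | 29% | 31% | 1,590 |

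The two base rates that fit the plan's own 159 give almost the same power. At other base rates the level shifts. With a higher rate of 0.30, for instance, 120 evaluable still give 81% and 80 give 64%.

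**Step 5. Compare with the plan's other minima.** Even with f = 100%, 160 is below 192 (Hypothesis 2, continuous), 208 (McNemar) and 300 (paired t-test). At 60% attrition these need 192/0.4 = 480, 208/0.4 = 520 and 300/0.4 = 750 enrolled per group. The 192 corresponds to about 90% power. At 80% power, d = 0.332 needs 143 per group, so valence in Hypothesis 2 tolerates f down to about 143/160 = 89%.

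**The case against.** **The 60% may already include silence.** Outcomes are captured passively, so going quiet is a natural form of attrition. If it is included, 160 per group remain evaluable and 159 is met. This stands. A reader might infer a certain shortfall, but the documents support only a conditional one.

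**Not every follower counts.** Section 6 screens followers and blocks those who do not qualify, so the point concerns eligible followers. It remains that the screening criteria omit the condition on which the two outcomes depend.

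**Silent followers are not without any outcome.** Section 2 also lists like, retweet and reply counts, and the measures table lists individual posting activity, for which zero is a valid value. A public follower who writes nothing can have these. The point is limited to valence and isolates, the outcomes for which sample sizes are given.

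**A reader might infer that silent followers become isolates automatically.** The description in Section 1 does not support this: with no Tweet, there is nothing to classify.

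**The unit of analysis is unclear.** The measures table puts valence and isolates at global network level, and Section 11 says analyses are aggregate. If the Tweet were the unit, silent followers would not reduce n in this way. Against that, the sample sizes count followers or users, and the paired t-test is described as within-subject. The documents conflict here.

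**The ceiling is not firm.** Section 7 gives more than 400 per group and an upper limit of 800 in one sentence.

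**Attachments are not shown.** A public-account condition in the screening scripts or network terms cannot be excluded.

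**Conclusion.** The concern holds in conditional form. Both powered outcomes require public Tweets, eligibility does not, and the allowance leaves one follower per group to spare. If the 60% excludes silent and protected accounts, and the follower is the unit of analysis, posting shares of 75%, 50% and 25% bring power for the isolate difference from about 80% down to about 69%, 51% and 29%. These shares are assumptions, and so are the base rates, which were chosen to agree with the plan's 159. If the 60% includes such accounts, the 159 is met, and what remains is an undefined attrition rate and an undefined evaluable follower.

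Hypothesis 1 is more exposed, because each pair needs Tweets in two windows and its minima of 208 and 300 already exceed 160.

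The documents do not support saying that power is certainly lost, that silent followers yield no data of any kind, or that the percentage of isolates is bound to track the share of readers.

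**What to change.** 1. State what the 60% covers: unfollowing, silence, protected accounts, or all of these.
2. At the existing screening step, check that the account is public.
3. Define an evaluable follower as one with a public account and at least one captured Tweet in each window the test uses. For the paired tests these are the 3-month baseline and months 9-12.
4. Count only followers who can be evaluable toward 400 per group. Posting in months 9-12 cannot be known at accrual, so the loss allowance must cover it explicitly.
5. Do not make posting an eligibility criterion. Section 6 would then have non-posting caregivers asked to unfollow and blocked, and a recent Tweet at screening would secure neither analysis window.
6. Keep the Section 1 meaning of isolate, so that a follower with no Tweets is missing and is not classed as an isolate.
7. Reconcile the statement of more than 400 per group with the limit of 800, and state the unit of analysis for valence and isolates.
8. If accrual cannot supply enough evaluable followers, restate the power for the number expected.

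The cost is a few definitions and a profile check by staff who already screen each follower. The downside is that formal results will describe caregivers who post publicly, which is already true for these two outcomes, and the stated power may become less favourable.
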